## 5.5 Study Evaluations

Experimental procedures:

After enrollment, the patients will be followed-up per clinical protocol. The study coordinator will collect clinical information regarding patient's medical therapy and the outcomes of interest and submit via eCRFs. The information will be collected through CPRS, and the coordinator may ask clarifying information from the subjects during their clinical visits. If care for the patient is provided at a non-VA hospital while enrolled in the study, the subject will be asked to sign a release of information form and relevant data collected from the corresponding medical records.

The patients will be asked to complete a short version of the Kansas City Cardiomyopathy Questionnaire (KCCQ-12) and a visual analogue scale (VAS) at the time of enrollment, at 30 days and at 90 days after enrollment or study exit if different than 90 days  $\pm$  7 days.

Qualitative research:

Up to 20 subjects enrolled in the randomized study will participate in a semi-structured interview that will examine their experience with the study procedures as part of a qualitative research part of the study. The interview will last 30 to 60 minutes.

As part of implementation research, up to ten clinicians of SLC VAMC and up to ten clinicians in each participating site will be approached to participate as clinician participants in cognitive task analysis before subject enrollment starts and in semistructured interviews after subject enrollment has initiated. The interview will last 30 to 60 minutes.

Authorization documents/cover letters will be read to the participants before the interviews to confirm their willingness to participate in the interviews. The interviews will be audio-recorded, transcribed, and analyzed.

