The initial device that the subject wears will be placed, and data collection started at the end of the in-hospital training session. Subsequently, additional adhesive patches (and replacement devices as needed) will be provided to subjects via mail by PhysIQ (along with a supply of adhesive remover wipes), and subjects will be asked to replace the device adhesive at home on their own whenever sent. Subjects will be provided with a technical support phone number to call for assistance.

Subjects will also be provided at this time with a smartphone that is paired with the wearable device and serves to receive data from the device and upload it to the analytics server via cellular network or WiFi internet. Subjects will be asked to return the smartphones at the end of the study during a routine clinical visit or in a prepaid mailer provided to them. Patients who complete the 90-days of telemonitoring will be given an option to keep the smartphone for their personal use (once all study related data is erased). Subjects will be provided with a technical support phone number to call for assistance. Subjects will be asked to wear the device as much as possible, with an ideal aim of near continuous data collection throughout study participation. However, it is anticipated that the subject may have acceptable periods of time when the device is not worn and data is not collected due to any of the following:

- Removing the device due to failing adhesive or to swap out a device.
- Removal of a depleted device while awaiting a replacement.
- Removal of the device for an interval for any reason of necessity of the subject (e.g., travel, procedure, etc.)

**Participant Follow up:** Subjects will participate in the trial for up to 90 days. Subjects will be mailed replacement adhesives as needed. Subjects will replace the adhesive themselves, per written take-home instructions. Data from the device will be uploaded in real-time and reviewed

by PhysIQ; in the event that data from the device indicates a problem with device function, placement or use, the subject will be called to confirm placement and use instructions.

[figure not shown]

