Should the subject damage, lose or have a malfunctioning study phone, a replacement will be provided to them at no expense. Such circumstances will not affect study participation nor incur any financial responsibility. However, if the subject has a pattern of losing the equipment generally it (phone /band aid) prevents acquisition of data and the study team may withdraw the subject.

After discharge from the hospital, the study staff will interact with the subject during follow-up visits scheduled for routine HF follow-up. Per clinical practice, the first clinic visit will be scheduled within 2 weeks of discharge. Subsequent study visits in the 90-day study period are expected to take place at day 30 and day 90 (+/- 7 days). If a face-to-face visit is not possible after a clinic visit the information will be obtained by calling the patient within the study visit window to address any study related questions, including device and phone functioning.

Additional encounters with providers will occur if alerts are generated based on remote monitoring data. The alert notification will be through the electronic health record (CPRS), and documentation of the response to the alert by the clinical team will also take place in CPRS. To reduce variation in response to clinical alerts, clinicians will follow a standardized response algorithm (**Figure 1**). Based on the remote monitoring data, clinical symptoms and blood pressure, the HF nurse will determine the suggested clinical action - medication up-titration, clinic visit, emergency room (ER) visit, or increase monitoring and confirm with the physician that this action should be implemented. In the control arm, information from the sensor will be collected, but clinical alerts will not be generated or communicated to the providers. Any treatment decisions will be made by the participant's clinical care team; the device only provides the alert and does not guide treatment. The research team will not be responding to the alarms. Of note, the remote monitoring data are not used for immediate decisions unrelated to the aims of the study. E.g., the device is not being used as an arrhythmia monitor and there is no real-time monitoring or clinician driven decision-making related to possible arrhythmias. In patients enrolled in the control arm, remote monitoring data are not being used for any clinical decisions. Patients are instructed to continue to seek care for their medical needs in the standard manner.

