## Status and Event Questionnaire

The questionnaire will be read to the subject by a member of the study team during the clinic visit or telephone call, and answers will be recorded in the electronic case report system. The questionnaire identifies medical events that the subject can recall and report for the interval since the last inquiry, including events that occur at health care facilities outside the clinical setting of the investigator's site and which may otherwise be unknown to the site clinical staff. Events may include acute care utilization or adverse events, in which case AE/SAE evaluations are triggered.

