An Adverse Event is any undesirable experience (as judged by the principal investigator) associated with the use of a medical product in a subject that is not judged to be serious. The event will be deemed a Serious Adverse Event and should be reported to the IRB as such when the subject outcome is: Death, Life-threatening, Hospitalization (initial or prolonged), Disability or Permanent Damage, Required Intervention to Prevent Permanent Impairment, or other serious events as judged by the principal investigator. (See for reference FDA definition at:

<http://www.fda.gov/Safety/MedWatch/HowToReport/ucm053087.htm>)

All events shall be reported as per institutional guidelines.

Medical record request to non-VA hospital or emergency department or clinic

In the event that an acute care episode (a primary event) occurs at a non-VA facility, medical records will likely be provided to the clinical team. In the unlikely situation that this does not take place, the subject will be asked to sign a medical record release form, and the study team will obtain the records in question. Relevant data will be entered into the electronic case report system. A subject may also sign the medical record release at the time of consent to cover any possible outside admissions during enrollment.

Determination of Exacerbation timing/Cause

In the event that an acute care episode (a primary event) occurs and is determined to be an exacerbation of a subject's chronic conditions, the site PI will make a determination of the timing and cause of the exacerbation.

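### Non-VA hospital admissions can be under-captured in the hospitalization estimates: outside records have no described route in, the release at consent is optional, and no contact is described after the day-90 window

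*Combined protocol and SAP*

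**What the plan says.** **Sources of events.** Section 5.0 (Experimental Procedures) limits the medical record review to events of interest within the VA system. It mentions the national VHA record (CAPRI/JLV) only for costs. Section 5.5 takes outcomes from CPRS and lets the coordinator ask subjects for clarification.

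**Outside events.** The Status and Event Questionnaire (section 6.0) records what the subject remembers from the period after the previous contact. Its stated reach extends to "events that occur at health care facilities outside the clinical setting of the investigator's site and which may otherwise be unknown to the site clinical" personnel.

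**Outside records.** Section 5.5: "If care for the patient is provided at a non-VA hospital while enrolled in the study, the subject will be asked to sign a release". Section 6.0 (Adverse Event and Serious Adverse Event) is worded differently. It expects the records to reach the clinical team and calls the opposite unlikely, and only then is a release sought. It adds: "A subject may also sign the medical record release at the time of consent to cover any possible outside admissions during enrollment".

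**Timing.** "Subjects will participate in the trial for up to 90 days". Section 5.0 places the last visit at day 90 with a 7-day margin on either side. If no face-to-face visit is possible, "the information will be obtained by calling the patient within the study visit window".

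**Use of the data.** Definition of Medical Events lists HF and all-cause hospitalization among the primary events. Section 5.6 plans Kaplan-Meier proportions with HF hospitalization for days 0-90, the 90 days after monitoring, and days 0-180. These are given by arm, with a risk ratio.

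**The concern.** Taken together, these passages leave three openings.

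- **Documentation.** An outside admission that does not reach the clinical team must be recalled by the subject and released under the subject's signature. A subject who has died, is incapacitated or cannot be reached can do neither, unless a release happened to be signed at consent. Section 5.6 allows for up to 25% loss to follow-up (0.25 × 240 = 60 subjects), so the unreachable group may not be small.
- **End of the 90-day window.** A last contact on day 83 complies with the plan, and outside admissions on days 84-90 may then never be asked about.
- **Days 91-180.** Estimates are planned, but no contact is described and the optional release covers enrollment only.

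Section 5.6 names HF hospitalization as the primary outcome of the future pivotal trial, so an under-counted rate would feed into its design. Hospitalization is also among the events tabulated for the DSMB at the interim analyses. A further issue is comparability: "Additional encounters with providers will occur if alerts are generated based on remote monitoring data", and alerts are issued only in the intervention arm. Clinicians may therefore hear of outside admissions more often in that arm.

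**Working it through.** **The plan's own figures.** Section 5.6 gives precision for the alert proportion and device time only, and these reproduce:
- 1.96 × √(0.25/240) = 0.063
- 1.96 × √(0.25/180) = 0.073
- 1.96 × 0.289/√180 = 0.042

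No event rate, non-VA share or precision is stated for hospitalization. The sizes below therefore rest on assumptions: a 90-day HF hospitalization risk p of 10-30%, a non-VA share f of 10-40%, and a constant hazard.

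**Step 1: calendar.** A last contact on day 83 leaves 7/90 = 7.8% of the window unasked. This is a share of time, and the worst case, since the margin also runs to day 97. For the 180-day estimate, (180 − 97)/180 = 46% to (180 − 83)/180 = 54% of the period lies after the last scheduled contact.

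**Step 2: the 7-day gap alone.** Suppose every subject is last seen on day 83 and all later outside first events are missed. Risk to day 83 is p83 = 1 − (1 − p)^(83/90), and the loss is f × (p − p83).
- At p = 0.20 and f = 0.25: p83 = 0.1860, so the loss is 0.25 × 0.0140 = 0.0035. That is 0.8 of 240 patients, or 1.8% of patients with an event.
- Over the full ranges: 0.2 to 1.9 of 240 patients, or 0.7% to 3.0% of patients with an event.

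**Step 3: earlier outside events also missed.** Let a share m of outside events before day 83 be missed. The loss is f × m × p83 + f × (p − p83).

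| p = 0.20, f = 0.25 | Loss | Observed risk | Share of patients with an event |
|---|---|---|---|
| m = 0.25 | 0.0116 + 0.0035 = 0.0151 | 18.5% | 7.6% |
| m = 0.50 | 0.0232 + 0.0035 = 0.0268 | 17.3% | 13.4% |

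Over the full ranges of p and f, with m from 0.25 to 0.50, about 3% to 21% of patients with an event are lost.

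**Step 4: 180 days.** Assume a 180-day risk of 20-40% and that all outside first events after day 90 are missed.
- At 30% risk and f = 0.25: risk to day 90 is 1 − √0.70 = 0.1633, so the loss is 0.25 × (0.30 − 0.1633) = 0.0342. The observed risk is 26.6%, with 8.2 of 240 patients lost (11.4% of those with an event).
- Over the ranges: 2.3 to 16.8 of 240 patients, or 4% to 19% of patients with an event.

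**Step 5: between arms.** If the same share of events is missed in both arms, the risk ratio is unchanged. Two illustrations of unequal loss, each with a true ratio of 1.00:
- 20% of admissions are non-VA, with a quarter missed under intervention and half under control: (1 − 0.20 × 0.25)/(1 − 0.20 × 0.50) = 0.95/0.90 = 1.06.
- 5% of all events missed under intervention and 15% under control: 0.95/0.85 = 1.12.

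For scale, at 20% risk with 120 per arm the standard error of the log risk ratio is √(2 × 0.8/(120 × 0.2)) = 0.258. The 95% interval around 1 is exp(±1.96 × 0.258), about 0.60 to 1.66.

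**The case against.** The plan is not silent on outside care. Section 6.0 treats the release as a fallback and allows it to be signed at consent. Hospitalization and death are serious adverse events with no VA-only limit, and hospitalizations are to be recorded, adjudicated and reported to the data coordinating center. Device data are reviewed throughout, and subjects are called about device problems in both arms. The visit schedule and questionnaire are the same in both arms, and the research team does not respond to alerts. The trial is a feasibility study, sized on the alert proportion and device time.

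Most of this stands, and it rules out several stronger readings that a reader might infer:
- *The endpoint depends on patient report and on a release usually signed after the event.* The plan names another route for the records and gives no frequency of signing.
- *The estimates are biased low, and it is the sickest patients who are lost.* The text supports only that they can be. Loss concentrated in the sickest is a plausible inference that the plan does not state.
- *A subject last seen on day 83 is counted as event-free to day 90.* No such rule appears. Kaplan-Meier estimates could censor on day 83, and the censoring date is simply not given.
- *The risk ratio is distorted.* The miss rates by arm are invented for illustration, and the shifts are small against an interval of about 0.60 to 1.66.

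These points do not close the gap itself. The expectation that records arrive has no process behind it, and the questionnaire section accepts that outside events may be unknown to site staff. The fallback still needs a signature. Adverse event reporting requires that someone first learn of the event.

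**Conclusion.** The concern holds as a risk of under-capture. The plan can be followed exactly and still miss non-VA admissions in a listed primary event. The days 84-90 gap is minor by itself. Of more weight are the incomplete route to outside records within the 90 days and the lack of any described contact behind the day 91-180 estimates. The sizes in the working are illustrations: the risks, non-VA shares and miss rates are all assumed, and the losses at 180 days suppose that every outside event after day 90 is missed. A difference in capture between arms is possible, of unknown size, and would probably be hard to see in a trial this small. Sections 5.5 and 6.0 also need reconciling on when the release is sought. This is a cheap improvement worth making; it does not invalidate the trial's feasibility aims.

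**What to change.** 1. **Release.** In section 6.0, replace the optional signature with a request to every subject at consent to sign the non-VA records release. It should cover the full analysis period, to day 180 if those estimates are kept. Edit section 5.5 to match. State how events will be sought for subjects who die or cannot respond. Whether the release remains usable in those cases cannot be judged from these documents.
2. **Close-out inquiry.** In section 5.0 and the Status and Event Questionnaire section, add a final questionnaire at day 90 to 97, by telephone if the last visit was before day 90, asking about events through day 90.
3. **Days 91-180.** Add a day-180 call, amending the 90-day participation statement accordingly, or name a record source for non-VA admissions. Otherwise limit those estimates, and their label, to VA admissions.
4. **Analysis rule.** In section 5.6, censor each subject for outside events at the last date through which they were asked about. Count outside admissions that are reported but undocumented as all-cause hospitalizations of unconfirmed cause, with a sensitivity analysis treating them as HF hospitalizations. Censoring avoids false event-free time but does not correct for loss related to illness, so report the number of subjects without a close-out inquiry by arm.

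**Cost.** One form at the existing consent visit, and a short call for subjects last seen before day 90. A second call is needed if the 180-day estimates keep outside admissions. A few subjects may decline the release.

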## 5.6 Data Analysis

HF hospitalizations will serve as the primary outcome in a pivotal trial of the effect of the remote monitoring intervention. A key parameter for determining the statistical power in a pivotal trial of the effectiveness of the intervention for this outcome and other secondary outcomes is the proportion of subjects who meet the algorithm's criteria for an alert, and thus may potentially be affected by the intervention. The statistical power of the pivotal trial will also depend heavily on the proper functioning of the remote monitoring. Accordingly, data analyses of our study will estimate the following quantities:

- 1) The proportion of randomized patients who meet the algorithm's criteria for at least one alert;

- 2) The ratio of the number of days the remote monitor is functioning properly (patient wearing device and data quality sufficient to make the daily decision) to the total number of days in the study;
- 3) The rate of HF hospitalization, all-cause hospitalization and LOS for those hospitalized;
- 4) Standard deviations and serial correlations for PRO outcomes (KCCQ, VAS);
- 5) The proportions of patients for whom the KCCQ and VAS fall within subgroups defined by the clinical cutoffs 0-≤25, 25-≤50, 50-≤75, 75-≤100;
- 6) The proportion of randomized patients who are lost to follow-up prior to day 90.

The proportions in items 1, 5 and 6 will be computed in the full randomized cohort with exact binomial 95% confidence intervals (CI). We will also use estimates based on Kaplan-Meier curves (see below) to provide the proportions of subjects with at least one HF hospitalization in the 90 days after enrollment, the 90 days after end of monitoring and the first 180 days by randomized group, with 95% CI for these proportions within each intervention group and for the risk ratio between the intervention and control groups. The ratio of actual vs. intended intervention time the monitor is on and functioning properly will be expressed as the proportion of days the remote monitor is functioning properly, and will be displayed for the full cohort, by randomized group, and by clinical site using box plots and histograms. Summary statistics will be provided to summarize the ratio of actual vs. intended intervention time over the full intervention period. Standard deviations and serial correlations for the patient reported outcomes will be estimated.

A total of 240 randomized subjects (60-125 will be recruited at the Salt Lake City VA) will be sufficient to estimate the proportion of subjects who experience at least one alert to within a margin of error (defined as the half-width of the 95% CI) of no more than  $\pm 0.063$  for an analysis of the full cohort. Assuming  $\leq 25\%$  loss to follow-up,  $\geq 180$  randomized subjects with complete follow-up will be sufficient to estimate the proportion of subjects who experience at least one alert to within a margin of error of no more than  $\pm 0.073$ .

The 240 randomized patients will also be sufficient to estimate the ratio of actual vs. intended time the device is on and functioning properly to within a margin of error of  $\pm 0.042$  assuming complete data on at least 75% of patients and conservatively assuming the standard deviation of this ratio does not exceed 0.289.

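### The alert-proportion margins are slightly too small for the exact intervals planned in section 5.6, and the standard deviation behind the uptime margin is not a guaranteed upper bound

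*Combined protocol and SAP*

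**What the plan says.** Section 5.6 (Data Analysis) of the combined protocol and SAP makes three precision statements.

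- **Alert proportion, full cohort.** "A total of 240 randomized subjects" are said to be enough to estimate the proportion with at least one alert "to within a margin of error (defined as the half-width of the 95% CI) of no more than" ±0.063.
- **Alert proportion, completers.** With up to 25% lost to follow-up, at least 180 patients remain, and the margin is given as no greater than ±0.073.
- **Uptime ratio** (share of days on which the monitor is worn and working). The margin is ±0.042, "assuming complete data on at least 75% of patients" and "conservatively assuming the standard deviation of this ratio does not exceed 0.289".

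Earlier in the same section the interval method is fixed for some quantities: "The proportions in items 1, 5 and 6 will be computed in the full randomized cohort with exact binomial 95% confidence intervals (CI"). Item 1 is the alert proportion. The uptime ratio is item 2 and is not in that list. For it, the section plans box plots and histograms, and adds: "Summary statistics will be provided to summarize the ratio of actual vs. intended intervention time over the full intervention period".

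**The concern.** The margin is defined as the half-width of the 95% interval and stated as a maximum, so it should hold for the interval the section specifies, whatever the alert proportion turns out to be. The plan assumes no alert rate, so proportions near 0.5 cannot be set aside.

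For uptime, calling the SD conservative tells the reader that the true value is very unlikely to be larger. But 0.289 equals 1/√12, the SD of a variable spread evenly over 0 to 1, and a 0-to-1 ratio can vary more than that.

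These margins are the only statistical justification for 240 patients in the documents. Section 5.6 also says that the power of the later pivotal trial depends on the alert proportion and on how well the monitoring functions. The stated precision of these two estimates should therefore be correct.

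**Working it through.** **Inputs, all from section 5.6:** n = 240; n = 0.75 × 240 = 180; 95% confidence (z = 1.96); SD 0.289; stated margins 0.063, 0.073 and 0.042.

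**1. Reproduce the plan's figures (normal approximation).**
- Alert, n = 240, p = 0.5: 1.96 × √(0.25/240) = 0.0633.
- Alert, n = 180, p = 0.5: 1.96 × √(0.25/180) = 0.0730.
- Uptime, n = 180: 1.96 × 0.289/√180 = 0.0422 (0.0425 with the t quantile).

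All three reproduce, so there is no slip in the arithmetic.

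**2. Apply the planned interval to the alert proportion.** Exact is taken as Clopper-Pearson. Half-widths were computed for every possible count.

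| n | Stated maximum | Exact maximum | Interval at the maximum | Observed proportions exceeding the stated limit | Wilson maximum |
|---|---|---|---|---|---|
| 240 | 0.063 | 0.0650 | 120/240: 0.435 to 0.565 | 0.375 to 0.625 | 0.0628 |
| 180 | 0.073 | 0.0753 | 90/180: 0.425 to 0.575 | 0.378 to 0.622 | 0.0723 |

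The excess is 0.0650 − 0.063 = 0.0020 and 0.0753 − 0.073 = 0.0023. If half-widths are rounded to three decimals before comparison, the stated limits are still exceeded from about 0.39 to 0.61. Outside the central range they hold: at n = 240 the exact half-width is 0.0598 for a proportion of 0.30 and 0.0525 for 0.20. For exact intervals to meet 0.063 and 0.073 at every proportion, n would have to be 256 and 192.

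**3. How large can the uptime SD be?**
- Uniform on 0 to 1: 1/√12 = 0.2887. This is the maximum for symmetric single-peaked shapes.
- Any single-peaked shape on 0 to 1: at most 1/3 = 0.333.
- Any distribution on 0 to 1 with mean m: at most √(m(1 − m)), which peaks at 0.5 when m = 0.5. This ceiling falls to 0.289 only if mean uptime is at least about 0.908 (or at most 0.092).

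**4. Uptime margin at n = 180, from 1.96 × SD/√180.**

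| SD | Margin |
|---|---|
| 0.289 | 0.042 |
| 0.333 | 0.049 |
| 0.35 | 0.051 |
| 0.40 | 0.058 |
| 0.50 (absolute maximum) | 0.073 |

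**5. Illustration (assumed, not from the documents).** With 70% of patients at 0.90 and 30% at 0.15, the SD is (0.90 − 0.15) × √(0.70 × 0.30) = 0.344 and the margin is 1.96 × 0.344/√180 = 0.050. Not every two-cluster pattern exceeds the plan's value: 75% at 0.85 and 25% at 0.20 gives 0.65 × √(0.75 × 0.25) = 0.281 and a margin of 0.041.

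**The case against.** **The interval gap is trivial.** It is about 0.002, arises only for central proportions, and comes from the common habit of planning with a normal approximation and reporting exact intervals. Section 5.6 also ties exact intervals to the full randomized cohort, so using them for the 180 completers is an inference. Exact is not further defined either; a mid-P version would give 0.0631 and 0.0728. All of this stands as a limit on importance. It does not rescue a stated maximum that the usual exact interval exceeds.

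**The uptime SD may well be adequate.** The true SD is unknown. The Introduction reports good compliance in the pilot, section 5.0 has device data reviewed in real time with calls to patients when problems appear, and section 6.0 allows patients who do not wear the device to be discontinued. The margin is also computed at the floor of 180 patients: with all 240, ±0.042 holds up to an SD of 0.042 × √240/1.96 = 0.332. These points make 0.289 plausible. They do not make it a ceiling, and the documents give no pilot SD. The protocol also foresees low-use patients (repeated loss of equipment, skin reactions, choosing not to wear the device). If they count against intended time, they form the kind of low cluster that can widen the spread.

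**Stronger readings that the documents do not support.** A reader might infer that all three margins fail under the exact intervals. They do not: those intervals cover items 1, 5 and 6, and uptime is item 2. A reader might also infer that all three rest on the doubtful SD, but only the 0.042 uses one.

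**Conclusion.** The point holds, as two separate and modest corrections.

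- **Alert proportion.** With Clopper-Pearson intervals the maxima are 0.065 at n = 240 and, if the same method is applied to the completers, 0.0753 at n = 180. The stated limits are exceeded by about 0.002 for observed proportions of about 0.38 to 0.62 and hold elsewhere. This changes no design decision.
- **Uptime.** The 0.042 is correct for its own inputs, but 0.289 is unsourced and is not a guaranteed upper bound. This is the more consequential part: at n = 180 the margin would be 0.051 to 0.058 for SDs of 0.35 to 0.40. The 0.073 needs half the patients at exactly 0 and half at exactly 1, so it is a bound and not a planning scenario.

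It would go too far to say that 0.289 is known to be too small, or that 240 patients are too few. The documents show neither. Aim 2 is feasibility estimation, and no test or decision threshold in section 5.6 depends on these margins.

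**What to change.** In section 5.6:

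1. **Alert proportion.** Either restate the margins as 0.065 (n = 240) and 0.076 (n = 180, rounded up so that the maximum holds), or specify Wilson intervals, whose maxima of 0.0628 and 0.0723 honor the stated figures. If Wilson is chosen, say whether it also replaces the exact method for items 5 and 6, which share the same sentence.
2. **Uptime.** Delete the word conservatively, or justify 0.289 with the observed SD from the pilot. In either case, state the margin at n = 180 over SDs of 0.289 to 0.40 (0.042 to 0.058), with 0.073 as the distribution-free bound.

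This takes about two sentences and adds no patients. The only cost is slightly less favorable stated precision.
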